#### 8.4. Protocol Deviations

The list of protocol deviations will be compiled prior to database lock. All deviations will be reviewed and decisions for handling each of the deviations will be made prior to the start of data analysis.

# 8.5. Demographics, Variables and Covariates

Age will be collected as a continuous measure, with all participants being ≥18 years of age. Age strata will be defined as stratum 1: 18–25 years old, stratum 2: 26–41 years old, stratum 3: 42–57 years old, stratum 4: 58–67 years old, stratum 5: 68–76 years old, stratum 6: 77–94 years old, 95+ years old. Age will be considered for secondary analysis.

Sex will be collected as a categorical variable: 0=male, 1=female, and 2=other. Sex will be considered for secondary analysis.

Left or right arm will also be documented for each SBP as will the information about which arm is the dominant arm. Dominant arm and left or right arm will be considered for secondary analysis.

Participants will be asked to complete a Fitzpatrick skin phototype assessment (scale I-VI). Skin phototype assessment will be considered for secondary analysis and primarily for the secondary endpoint for questions regarding the ability to visually see the SBP(s) on the skin.

#### 8.6. Derived Variables

The difference between volar forearm and inner elbow measurements will be calculated for each timepoint.

Degradation Rate will be calculated as =  $(C_o - C_t) / C_o$ , where  $C_o$  is the original Corneometer® measurement value and  $C_t$  is the Corneometer® measurement at a given follow-up timepoint. We will be looking to see when the degradation rate reaches 50%.

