daily readings for the first 72 hours, which is the more important window to evaluate SBP wear time. There will be a two-day break in measurements over the weekend, after which Corneometer® measurements will be taken either on Monday, or Monday and Tuesday, depending on the participants' start date. Participants will be allowed to bathe their arms using a standardized soap provided by the study personnel but will be asked to minimize scrubbing and any other abrasion of the volar forearms and inner elbows. In addition, participants will be instructed not to engage in activities, for eg, sports (eg, tennis) or holding a baby that may cause significant abrasion on one arm and not the other. On the last visit of the study (Visit 6), study personnel will take the last set of Corneometer® measurements. In addition, participants will also complete surveys regarding their experience with the SBPs on specific days during study participation.

The Corneometer® measurements will help determine the presence of the SBPs and their deterioration over time. Skin treated with the SBPs will typically have lower readings than untreated skin. As the SBPs break down, the corresponding readings are expected to rise.

**Study Duration:** Up to three months.

**Participant Duration:** Up to 13 days.

Version 2.0 CONFIDENTIAL Page 9 of 28

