wrist), and baseline Corneometer® measurements will be taken. Per the Randomization Schedule. each participant will be assigned to either Marathon® or Cavilon™ (designated SBP). The designated SBP will be applied to the volar forearm and inner elbow "test areas" on the participants' dominant arm (as determined by the participant). The other SBP will be applied to the volar forearm and inner elbow "test areas" on the participants' non-dominant arm. A distinct area of each volar forearm of the participants will be used as an "untreated control area" for the test areas on that forearm. To assess baseline skin hydration, study personnel will use the Corneometer® to take the average of five initial measurements of skin capacitance and the standard deviation of the measurements, for each of the untreated control areas and the volar forearm and inner elbow test areas. After the baseline measurements have been recorded, the study personnel will apply the two SBPs, Marathon® and Cavilon™, according to the Randomization Schedule to test areas on the participants' volar forearm and the inner elbow. After the SBPs have been left to dry for at least one minute or have dried completely, Corneometer® measurements will be repeated in the untreated control areas and the volar forearm and inner elbow test areas in a manner similar to the baseline measurements. Thereafter, daily Corneometer® measurements will be taken over a seven-day period with a two-day break over the weekend. During the study period, participants will be allowed to bathe their arms using a standardized soap provided by the study personnel but will be instructed to minimize scrubbing or any other abrasion of the skin of the volar forearms and inner elbows. In addition, participants will be instructed not to engage in activities, for eg, sports (eg, tennis) or holding a baby that may cause significant abrasion on one arm and not the other. On the last day of the study (Visit 6), study personnel will take the last set of Corneometer® measurements. In addition, participants will complete surveys regarding their experience with the two SBPs on specific days during study participation.

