#### Note:

- 1. Skin treated with the SBPs will typically have lower measurements than untreated skin. As the SBP breaks down, the corresponding measurements are expected to rise.
- 2. Each participant will commence the study on Monday or Tuesday, which will permit daily readings for the first 72 hours, which is the more important window to evaluate SBP wear time. There will be a two-day break over the weekend, after which study personnel will take Corneometer® measurements either on Monday, or Monday and Tuesday, depending on the participant's start date.

Version 2.0 CONFIDENTIAL Page 14 of 28

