# 6.2.3 Application of Skin Barrier Protectants (SBPs) and Corneometer® Measurements

Study personnel will draw 2-inch x 2-inch squares on the participants' forearms for each untreated control area and each test area using a non-toxic marker, such that three squares are marked on each volar forearm and inner elbow taken together. The lower squares on the volar forearms (LL and LR) will be marked about two inches above each wrist and will be used as untreated control areas. The upper squares on the volar forearms (UL and UR) will be used as test areas. The squares marked on the inner elbows of the participants (LIE and RIE) will be used as test areas as well. Refer to Figure 6.2.2 for details.

To measure baseline skin hydration, study personnel will use the Corneometer® to take the average of five measurements of skin capacitance and the standard deviation of the measurements for both the left and right forearm within each of the untreated control areas and volar forearm and inner elbow test areas. The Corneometer® measurements will be recorded in the CRF.

After the baseline measurements have been taken, study personnel will apply a thin layer of either Marathon ® or Cavilon TM (per the Randomization Schedule), such that the SBP covers the participants' skin within the border of the volar forearm and inner elbow test area squares. Each volar forearm will also include a 2-inch x 2-inch untreated control area square where no SBP will be applied. The participants will not be informed about the type of SBP applied to the volar forearm and inner elbow test areas. The participants will be instructed not to leave the study room, and that their forearms must remain exposed such that no article of clothing comes in contact with their forearms and inner elbows.

After the SBPs have been left to dry for at least one minute or have dried fully, Corneometer® measurements will be repeated in a manner similar to the baseline measurements, for each of the two untreated control areas and four test areas. The average of the Corneometer® measurements and the standard deviation of the measurements will be recorded in the CRF.

Participants will be dismissed from the study room and will be instructed to return the next day (within a  $24 \pm 4$  hours window) for Visit 2.

Medline Industries, LP
An evaluation of the skin protection characteristics of two commercially available skin barrier protectants
MED-2022-DIV71-003
08-AUG-2022

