# **Analysis of Primary Endpoints**

# 8.8.1. Primary Endpoints

Degradation of the SBP over seven days as measured by the Corneometer®.

The breakdown of the SBPs on the volar forearm test areas will reflect the duration of wear of the SBPs. Independent sample t-tests or non-parametric equivalent tests will be used to compare mean Marathon® and Cavilon™ Corneometer® values at baseline (Visit 1), Visit 2, Visit 3, Visit 4, Visit 5, and the final Visit 6 for untreated control area and volar forearm test area measurements. Paired-sample t-tests will be used to compare any two data points for a given SBP and location.

The breakdown of the SBP on the inner elbow test area, relative to the corresponding volar forearm test area, will reflect the durability of the products. Derived variables will be created to calculate the difference between the volar forearm test area measurement and the inner elbow test area measurement at baseline (Visit 1), Visit 2, Visit 3, Visit 4, Visit 5, and the final Visit 6. Independent sample t-tests or non-parametric equivalent tests will be used to compare mean Marathon® and Cavilon™ Corneometer® difference values at baseline (Visit 1), Visit 2, Visit 3 and the final Visit 6 on Day 8. Paired-sample t-tests will be used to compare any two data difference points for a given SBP.

Both degradation and durability endpoints will be graphed across time by SBP with and without 95% confidence intervals of the mean.

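### The Section 8.6 Degradation Rate falls as product is lost, so its 50% point is mislabelled and is reached either downward or not at all, depending on which Visit 1 reading is Co

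*Combined protocol and SAP*

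**What the plan says.** Section 8.6 (Derived Variables) states that "Degradation Rate will be calculated as" (Co − Ct)/Co, where Co is the original reading and Ct is the reading at a follow-up timepoint. It then gives the purpose: "We will be looking to see when the degradation rate reaches 50" per cent.

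The expected direction of the readings is given twice. Section 4.1, Note 1, says "Skin treated with the SBPs will typically have lower measurements than untreated skin" and then "As the SBP breaks down, the corresponding measurements are expected to rise". The synopsis agrees: "As the SBPs break down, the corresponding readings are expected to rise".

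Visit 1 gives two readings per square. Section 4.1 describes the pre-application set as "the average of five initial measurements of skin capacitance". After the product has dried, Section 6.2.3 says that "measurements will be repeated in a manner similar to the baseline measurements, for each of the two untreated control areas and four test areas". Section 8.6 does not say which of the two is Co. Section 8.8.1 compares mean readings "at baseline (Visit 1), Visit 2, Visit 3, Visit 4, Visit 5, and the final Visit 6", and does not separate the two Visit 1 readings.

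**The concern.** A quantity called degradation should rise as the product degrades. This one has the follow-up reading subtracted in the numerator, and the protocol expects that reading to rise, so a higher value means more product left. Waiting for it to reach 50% also suggests an upward crossing, which the expected course of the readings does not produce.

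The primary objective is to compare duration of wear and durability. The Section 8.8.1 tests compare means at visits, or between visits, and do not yield a time. The 50% criterion is the only place where the plan would say how long a product lasts. If its direction, its reference reading and the handling of squares that never cross stay open until the data are in, those choices become post hoc.

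**Working it through.** **The plan's own computed figure.** The only computed design figure is N = 42 in Section 8.1. A paired t-test for superiority by a margin, with mean difference 17.5, margin 15 (net 2.5), SD 5.05 and one-sided α = .0125, has noncentral-t power .796 at n = 41 and .807 at n = 42. This reproduces 42. No 8.6 quantity enters it.

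**Inputs.** The formula is from 8.6 and the direction from Section 4.1, Note 1. The documents give no baseline or fresh-film readings, so r below is an assumption shown over a range.

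**Step 1, direction.** With R = (Co − Ct)/Co, dR/dCt = −1/Co, which is negative for any positive Co. R falls as Ct rises, whichever Visit 1 reading is Co. No assumed data are needed.

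**Step 2, size.** Set baseline to 1 and the fresh-film reading to r (below 1). Let λ be the fraction of the film signal lost, so Ct = r + λ(1 − r).

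- Pre-application Co: R = (1 − r)(1 − λ). It starts at 1 − r and ends at 0. R = 50% means Ct = Co/2, at λ = (0.5 − r)/(1 − r). This needs r ≤ 0.5; at r = 0.5 the index starts at exactly 50%.
- Post-application Co: R = −λ(1 − r)/r. It starts at 0 and goes negative.

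| Assumed r | Pre-application Co: R at 0 / half / all signal lost | Signal lost when R = 50% | Post-application Co: R at 0 / half / all signal lost |
|---|---|---|---|
| 0.10 | 90% / 45% / 0% | 44% | 0% / −450% / −900% |
| 0.25 | 75% / 37.5% / 0% | 33% | 0% / −150% / −300% |
| 0.45 | 55% / 27.5% / 0% | 9% | 0% / −61% / −122% |
| 0.60 | 40% / 20% / 0% | no crossing | 0% / −33% / −67% |

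For example, at r = 0.45 the crossing is at (0.50 − 0.45)/(1 − 0.45) = 0.05/0.55 = 9%. Even where a crossing exists, it does not mark half the film signal lost, and the share lost at that point changes with r.

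**Step 3, a loss index.** L = (Ct − Cpost)/(Cbase − Cpost) equals λ by construction. It runs from 0 to 1 and reaches 0.5 at half the signal lost for every r. Its threshold in absolute readings is (Cbase + Cpost)/2. With an assumed baseline of 40, that is 22.5 if fresh film reads 5 and 30 if it reads 20, whereas reduction remaining always meets 50% at 20. At a shared reading of 25, L is 20/35 = 57% and 5/20 = 25%, while reduction remaining is 15/40 = 37.5% for both. The two measures answer different questions.

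**Step 4, timing.** Section 8.8.1 places Visit 6 on Day 8, so Visit 1 is Day 1. A Monday start then has visits on Days 1, 2, 3, 4, 5 and 8. A Tuesday start has them on Days 1, 2, 3, 4, 7 and 8. The weekend gap is Day 5 to 8 or Day 4 to 7.

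**The case against.** The strongest reply is that little depends on this. No test in 8.8.1 names the Degradation Rate; at most, the planned graph of degradation over time might use it. Section 8.6 attaches no hypothesis, significance level or summary method to the 50% point. That stands: it is a descriptive derived variable, and a reader who infers that the primary comparisons or the sample size are compromised would be wrong, because they rest on raw readings, forearm–elbow differences and the Section 8.1 inputs.

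A reader might also infer that the 50% time cannot be computed. The documents do not support that. The pre-application set is the one described as initial and the post-application set as repeated, so pre-application is the natural meaning of original. On that reading the index is computable but mislabelled, with a well-defined downward crossing whenever r is below 0.5. Section 8.1 mentions internal data but gives no reading levels, so nobody can say from the documents how often r exceeds 0.5.

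Nor does 8.6 yield two competing 50% times. In the expected direction, pre-application Co gives one time or none, and post-application Co gives none. The different thresholds in Step 3 compare the plan's index with a proposed replacement; they are not two readings of 8.6.

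What the reply does not remove is the conflict between the formula and the expected direction of the readings. Nothing elsewhere in the plan repairs it.

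**Conclusion.** The point holds and should be fixed before data are seen. The inversion follows from the plan's own text and needs no assumed values. The size of the effect on the 50% point does depend on assumed r, and the absence of a crossing is conditional on r above 0.5, or on Co being the post-application reading. These results also assume that readings rise steadily from the fresh-film value, as the protocol expects; noise or drift in skin hydration could produce stray crossings. The consequence is confined to the descriptive wear-time readout.

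**What to change.** In Section 8.6:

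1. Name both Visit 1 readings: Cbase (pre-application) and Cpost (post-application). Define loss per square as L_t = (C_t − Cpost)/(Cbase − Cpost), and state that 50% means half of that square's own initial signal drop has been lost.
2. Because L_t is relative to each product's own drop, also report (Cbase − C_t)/Cbase under the label percentage reduction remaining. State that it crosses 50% downward, and how many squares are already below 50% at application.
3. Report the first visit interval in which L_t reaches 0.5, right-censored at Visit 6. Use the protocol's day numbering, and keep the weekend as one interval: Day 5 to 8 for a Monday start, Day 4 to 7 for a Tuesday start.
4. Count squares with Cpost ≥ Cbase by product, as having no measurable film signal at application, rather than dropping them.

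Optionally, tabulate the change in the same-forearm control square by visit as a check on bare-skin drift. The inner elbow has no control square, so this covers the forearm only.

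Cost: a wording change and a little extra programming. Every reading needed is already scheduled and recorded. L_t is noisy when the initial drop is small. With drop D and error s in each five-reading mean, its standard error near 0.5 is √1.5 × s/D, which is 0.41 at D = 3s and 0.12 at D = 10s, before any day-to-day variation. Its absolute threshold also differs by product, which is why both measures should be shown.

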### 8.7. Handling of Missing Values

All missing data will be quantified in the final report and possible biases for any missing data will be reported.

### 8.8. Statistical Analysis

Statistical analyses will be conducted in SAS® software, Version 9.4 or higher of the SAS System for Windows (Copyright © 2013 SAS Institute Inc.) or other appropriate statistical software. P < .05 will be considered statistically significant.

All continuous variables will be summarized for the full sample and by SBP group using the following descriptive statistics: (non-missing sample size), mean, standard deviation, median, maximum and minimum. The frequency and percentages (based on the non-missing sample size)

Medline Industries, LP
An evaluation of the skin protection characteristics of two commercially available skin barrier protectants
MED-2022-DIV71-003
08-AUG-2022

Version 2.0 CONFIDENTIAL Page 23 of 28

of observed levels will be reported for all categorical measures. 95% confidence intervals will be calculated for all means.

Spearman correlation analysis will be used to examine possible associations between the key variables of Marathon® or Cavilon™ use and the Corneometer® measurements at various timepoints with covariates of age, sex, and dominant arm. Additional t-tests or non-parametric tests will be employed to further examine any significant associations found in the correlational analyses between key and covariate measures.

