#### 8. STATISTICAL CONSIDERATIONS

#### 8.1. Sample Size Determination

A sample size of 42 was elected for a superiority margin of at least 15 arbitrary capacitance units  $(A.C.U)^{10}$  as measured by the Corneometer® with an estimated mean of pair differences of 17.5 and the standard deviation of 5.05, given the 80% power at Bonferonni adjusted significance level of  $\alpha = .0125$ . Internal evaluation SBP data was used as a starting point, and PASS- Paired T-Tests for Superiority by a Margin procedure was utilized for the sample size estimation (PASS 2021 Power Analysis and Sample Size Software (2021). NCSS, LLC. Kaysville, Utah, USA, ncss.com/software/pass).

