#### 8.2. Randomization

This is a single-blind study, with participants blinded to the SBPs that are applied to them. Due to the primary focus on durability of the SBPs, randomization will target dominant versus non-dominant arms, not left versus right. Participants will be randomized to either Marathon® or CavilonTM, and this SBP will be applied to their dominant arm, as defined by the participant. This ensures an equal probability of Marathon® and CavilonTM on both dominant and non-dominant arms. If a participant has incomplete data, the participant will be replaced such that the randomization sequence of the replaced participant will be assigned to the new participant.

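### Arm dominance, the factor used for randomization, is missing from the product comparison and left to a Spearman screen that either ignores or discards the pairing of arms

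*Combined protocol and SAP*

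**What the plan says.** Section 8.2 explains the allocation: "Due to the primary focus on durability of the SBPs, randomization will target dominant versus non-dominant arms, not left versus right". Section 6.2.2 adds that each participant receives both products, one per arm, with equal chance of either product being on the dominant arm.

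Section 8.1 sizes the trial on within-participant differences: "Paired T-Tests for Superiority by a Margin procedure was utilized for the sample size estimation".

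Section 8.8.1 compares the products at each visit with independent-sample t-tests or non-parametric equivalents. No term for dominance or participant appears. Section 8.5 lists dominance, age and sex for secondary analysis without a method.

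The only method is in 8.8, where Spearman "correlation analysis will be used to examine possible associations between the key variables" (product use and Corneometer readings) and age, sex and dominant arm. It continues: "Additional t-tests or non-parametric tests will be employed to further examine any significant associations found in the correlational analyses". The general threshold in 8.8 is P < .05. On sex, 8.5 says: "Sex will be collected as a categorical variable: 0=male, 1=female, and 2=other".

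**The concern.** The plan treats dominance as important enough to randomize by, then leaves it out of the comparison that the randomization serves. Replacing the independent-sample tests with a plain paired t-test would not cure this, because any dominance effect would remain in the spread of the differences.

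The Spearman screen does not fill the gap. Product use can vary as a correlation variable only if both arms are in the data set, so pooling 84 rows from 42 people is the natural reading, although 8.8 does not say so. Spearman then treats a participant's two arms as unrelated. Under the other reading, one correlation per product, each participant contributes one reading; dominance becomes a comparison between different people and the pairing is lost.

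At stake are the precision of the product comparison, the ability to see a dominance effect, and the trustworthiness of any reported age or sex association. Spearman would also rank the sex codes as if the third category lay above the other two.

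**Working it through.** **Inputs from 8.1.** "A sample size of 42 was elected for a superiority margin of at least 15 arbitrary capacitance units", with "estimated mean of pair differences of 17.5 and the standard deviation of 5.05", "given the 80% power at Bonferonni adjusted significance level of" .0125.

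**Assumptions, not in the documents.** Correlation between a participant's two arms, rho = .3, .5 or .7. Dominance effect δ (dominant minus non-dominant arm, same product) = 2 or 3 A.C.U. A 21/21 split unless stated.

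**Step 1: reproduce n = 42.** The effect beyond the margin is 17.5 − 15 = 2.5. The noncentrality is 2.5 × √42 / 5.05 = 3.21 on 41 degrees of freedom. At one-sided .0125 the power is 80.7%, and 42 is the smallest n reaching 80%. Sidedness is not stated; two-sided .0125 would give 72.2% at n = 42.

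**Step 2: cost of omitting dominance in that test.** A participant's difference is the product effect plus δ or minus δ, according to allocation. If 5.05 excludes dominance, the SD without the term is √(5.05² + δ²).

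- δ = 2: SD 5.43, power 74.2%.
- δ = 3: SD 5.87, power 66.7%.
- δ = 0 with the term included: 80.66% against 80.72%.

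If 5.05 already contains the dominance effect, planned power stays 80.7% without the term. With it, the SD falls to √(5.05² − δ²) = 4.64 or 4.06 and power rises to 87% or 95%.

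**Step 3: the screen.** The SD of a single reading is 5.05 / √(2(1 − rho)) = 4.27, 5.05 or 6.52. With equal products and pooled arms, the true two-sided error of a nominal 5% test is about 2[1 − Φ(1.96/√(1 + rho))] for age or sex: 8.6%, 11.0%, 13.3%. For dominance the divisor is √(1 − rho), giving 1.9%, 0.6%, 0.03%; simulation gives about 2%, 0.8% and 0.1%. When the products differ by 17.5, every participant has one high and one low reading. The pooled spread grows and the tests become too strict. Simulated results with 42 participants:

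| Nominal 5% test | rho .3 | rho .5 | rho .7 |
|---|---|---|---|
| Pooled, age, no age effect, products equal | 9% | 11% | 13% |
| Pooled, age, no age effect, products differ by 17.5 | 0.1% | 0.1% | 0.8% |
| Pooled, power for δ = 3, products equal | 91% | 82% | 57% |
| Pooled, power for δ = 3, products differ by 17.5 | 14% | 5% | 1% |
| By product, age or dominance, no effect | 5% | 5% | 5% |
| By product, power for δ = 3 | 59% | 45% | 30% |
| Paired difference regressed on allocation, power for δ = 3 | 96% | 96% | 96% |

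The last row does not depend on rho: the standard error is 5.05/√42 = 0.779, and 3/0.779 = 3.85.

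**Step 4: uneven split.** No blocking is stated. Under simple randomization the 95% range for one allocation is 15 to 27 of 42. At 27/15 the unadjusted product difference shifts by (27 − 15)/42 × δ, which is 0.86 A.C.U. for δ = 3.

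**The case against.** The case against has real force on several points.

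- **Pooling is not stated.** If the correlations are run by product, error rates are about right and only power is lost. This stands, so the error-rate criticism is conditional.
- **Direction of the error.** A reader might infer that the screen will produce too many false age or sex findings. That holds for pooled arms when the products differ little, for example at baseline. At the planned 17.5 A.C.U. difference the pooled age test is far too strict instead.
- **Bias.** A reader might infer that leaving dominance out biases the product comparison. Randomization balances it on average, so it does not. A shift needs an uneven realized split. The Randomization Schedule is a separate document and may force 21/21; because replacements inherit the sequence (5.4, 8.2), such a split would survive among completers.
- **Size of the effect.** No dominance effect is given. Sections 5.2 and 6.3.1 exclude people with, and tell participants to avoid, activities that load one arm, which limits it. The power loss also requires that 5.05 excludes dominance.
- **Age and sex on the paired difference.** It is tempting to move every covariate to the Marathon-minus-Cavilon difference. An age effect common to both arms cancels there, leaving only modification of the product effect. Section 8.8 asks about association with the readings, so the difference alone would drop the planned question.
- **Sex codes.** If only 0 and 1 occur, Spearman is in effect a rank test of two groups. The ordering matters only if code 2 is used.

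The independent-sample tests in 8.8.1 are a separate defect in the same comparison. None of these points gives a reason to leave the allocation factor out of the analysis.

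**Conclusion.** The concern holds in conditional form and should be fixed before analysis. The product comparison omits the factor by which product was allocated, and neither reading of the Spearman screen makes up for it. Pooled, its error rates are wrong in a direction set by the product difference, and at the planned difference it has about 14% power or less for a 3 A.C.U. dominance effect. Run by product, its error rates are sound but its power is 30 to 59%, where the paired data give about 96%.

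For the product comparison the consequence is lost precision: 80.7% falls to 74% or 67% if the effect is 2 or 3 A.C.U. and lies outside the 5.05. It is not bias on average. Rho and δ are assumptions, so these figures show a range and do not predict what this trial will find.

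**What to change.** **Product comparison.** At each visit, regress each participant's Marathon-minus-Cavilon difference on allocation, coded +1 if Marathon is on the dominant arm and −1 if not. The intercept is the product effect adjusted for dominance; the slope is the dominance effect. Use the same model for the volar forearm reading and for the forearm-minus-elbow difference.

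**Age and sex.** Replace the Spearman paragraph with prespecified exploratory analyses at n = 42, with age continuous and sex as categories. Use the participant's mean over both arms for association with the readings, and the within-participant difference for modification of the product effect. Report all of them whatever the p-value.

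A mixed model with a participant random effect and product, dominance, age and sex terms is an equivalent route; modification of the product effect then needs product-by-age and product-by-sex terms.

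**Cost.** SAP wording and one degree of freedom in the product comparison (80.66% against 80.72% power if dominance has no effect). No extra data, visits or participants are needed.

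### Section 8.8 re-tests whatever passes a P < .05 covariate screen on the same participants, with no multiplicity control and no exploratory label

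*Combined protocol and SAP*

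**What the plan says.** Section 8.8 (Statistical Analysis) sets one general threshold: "P < .05 will be considered statistically significant". It plans Spearman correlations of product use and Corneometer "measurements at various timepoints with covariates of age, sex, and dominant arm". It does not name the timepoints or sites, or say whether the correlations are run separately by product. The next sentence makes the later tests depend on the result: "Additional t-tests or non-parametric tests will be employed to further examine any significant associations found in the correlational analyses between key and covariate measures".

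Section 8.5 describes the covariates one at a time: "Age will be considered for secondary analysis"; "Sex will be considered for secondary analysis"; "Dominant arm and left or right arm will be considered for secondary analysis"; and, for phototype, "Skin phototype assessment will be considered for secondary analysis and primarily for the secondary endpoint". Left or right arm and phototype are therefore additional to the three covariates named in 8.8.

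Section 8.8.1 lists the visits at which readings are compared between products: "at baseline (Visit 1), Visit 2, Visit 3, Visit 4, Visit 5, and the final Visit 6 for untreated control area" and for the volar forearm test area, with inner elbow differences handled separately.

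The only multiplicity adjustment in the documents is the Bonferroni level of .0125 in the sample size statement (8.1). Section 8.8 does not carry it forward. No section calls the covariate analyses exploratory, limits their number or orders them.

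**The concern.** Two features combine. First, the screen is a family of tests of unstated size at an unadjusted .05, so the chance of at least one false association is well above 5%. Second, the follow-up test is run because the same data already showed the association. It will often be significant again even when the association is pure chance.

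A clinical study report could then state that readings depend on sex, on arm dominance or on age, and support this with two significant tests. A reader would naturally take the second as corroboration. Section 2.3.2 says that the study's information may inform the clinical use decisions of healthcare providers, so a chance finding presented in this way could be acted on.

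**Working it through.** **Inputs from the documents.** N = 42 (8.1); three covariates, threshold .05 and follow-up t-tests or non-parametric tests (8.8); six visits and two products (8.8.1).

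**The plan's own figure.** The plan gives no error rate for the covariate screen. Its sample size does reproduce: a paired t-test with mean difference 17.5 - 15 = 2.5, SD 5.05 and one-sided alpha .0125 gives N = 42, with exact power 80.7%. This confirms the design N used below and has no other bearing on the screen.

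**Assumptions, because the documents are silent.** Age is uniform over about 18-67 or 20-65 years and split into two groups for the follow-up test. Sex is split 21:21, and so is the assignment of a given product to the dominant arm. Readings are normal and unrelated to any covariate. Two grids are used:
- 18 tests: 3 covariates x 6 visits, one product, one site.
- 30 tests: 3 covariates x 2 products x 5 follow-up visits, forearm only.

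**Step 1, upper reference.** If the k tests were independent, P(at least one P < .05) = 1 - 0.95^k.
- k = 18: 1 - 0.95^18 = 60.3%
- k = 30: 1 - 0.95^30 = 78.5%
- For comparison, one test per covariate, k = 3: 1 - 0.95^3 = 14.3%

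**Step 2, correlated readings.** Readings on the same skin across visits are correlated, which lowers these figures. Null simulation, with a Spearman screen at .05 followed by a two-sample t-test at .05 on each hit:

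| Tests | Correlation between readings | Any screen hit | Any hit also significant on t-test | Ratio |
|---|---|---|---|---|
| 30 | 0.2 | 78% | 63% | 63/78 = 81% |
| 30 | 0.5 | 65% | 53% | 53/65 = 82% |
| 30 | 0.8 | 49% | 37% | 37/49 = 76% |
| 18 | 0.5 | 52% | 40% | 40/52 = 77% |
| 18 | 0.9 | 32% | 23% | 23/32 = 72% |

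The 30-test rows rest on 1,000 simulated trials each (standard error about 1.5 percentage points) and the 18-test rows on 6,000. Rounded outward, the ranges are 30-80% for the screen and 20-65% for double significance.

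Larger grids raise the screen figure. With 36 tests (six visits, two products) it runs from 42%, when visits and arms are both correlated 0.9, to 85% under independence. With both sites (72 tests) it is 73-92%.

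**Step 3, how often a chance hit recurs on the same data.**

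| Covariate | t-test | Rank-sum test |
|---|---|---|
| Sex, dominant arm | about 78% (75-82% across runs) | about 94% |
| Age, two groups | about half | about half |

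A re-test in new participants would be significant 5% of the time. The rank-test figure has a simple cause. With a two-level covariate, Spearman's coefficient and the rank-sum statistic both depend only on the difference in mean ranks, so they are almost the same test. They disagree only near the threshold, where their P-value approximations differ. For age, the screen uses the full ordering and the follow-up a two-group split, so agreement is weaker.

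**The case against.** The case against is substantial, and much of it stands.

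- **The plan claims no confirmation.** Section 8.8 speaks of examining possible associations and 8.5 of secondary analysis. No objective or endpoint in section 3 involves age, sex or arm. A reader might infer that the second test is offered as confirmation; the documents do not say so. It could equally be meant to restate a correlation as a group difference. The wording still does not amount to an exploratory label: the significance rule in 8.8 has no exception, and significance is what triggers the next test.
- **The number of tests is assumed.** The timepoints, sites and split by product are all unstated. A reader might infer that a doubly significant false finding is more likely than not. That holds in some settings (53% with 30 tests at correlation 0.5) and fails in others (37% at 0.8; 23% with 18 tests at 0.9). High correlation is plausible, because the same marked squares are measured repeatedly over about a week.
- **Recurrence is not uniform.** It is the usual outcome for sex and dominant arm, but for age it is close to even. The two-group age split is also an assumption, since 8.5 defines several strata.
- **These are not subgroup findings.** The plan correlates covariates with readings. It does not test product effects within subgroups or product-by-covariate interactions.
- **The main result is untouched.** The product comparison in 8.8.1 does not pass through this screen.

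These points limit how strongly the matter can be put. They do not remove it: even the lowest screen figure, 32%, is about six times the nominal 5% (32/5 = 6.4).

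**Conclusion.** The point holds as a reporting weakness that is cheap to repair. Section 8.8 selects covariate associations at an unadjusted .05 from an unspecified number of correlations and re-tests the selected ones on the same participants, with no exploratory label. Under the assumed grids of 18 to 30 tests and between-reading correlations of 0.2 to 0.9, a trial with no true association yields at least one significant screen roughly 30-80% of the time and a doubly significant one roughly 20-65% of the time. The width of these ranges reflects what the plan leaves open. The lack of independence between the two steps is firmer, because it follows from the tests chosen. The documents do not support saying that a false finding is more likely than not, that every chance hit will usually recur, or that the comparison of the two products is compromised.

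**What to change.** In section 8.8, state that the age, sex and dominant arm association analyses, and the left/right arm and phototype analyses mentioned in 8.5, are exploratory; that they are run separately by product at all visits and sites listed in 8.8.1; and that all of them are reported as estimates with 95% confidence intervals, with no claim of statistical significance. Delete the sentence that sends significant correlations to further t-tests or non-parametric tests.

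It may be tempting to replace the whole set with one analysis per covariate of the within-participant difference between products at a single visit, such as Visit 4. That would answer a different question. An age or sex effect common to both arms cancels in the difference, so the dependence of readings on age or sex that 8.8 sets out to examine could not be seen. It would also drop the inner elbow and the other visits. The planned associations should stay, with the label and full reporting.

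The cost is SAP wording only, with no new data, visits or participants. The downside is small: covariate findings become hypothesis-generating and cannot be reported as significant.
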